14.7 SERIOUS ADVERSE EVENTS

Each adverse event or reaction will be classified by the study investigator as serious or nonserious. Based on the seriousness of the adverse event or reaction appropriate reporting procedures will be followed. The International Conference on Harmonization (ICH) Guideline for Industry: Clinical Safety Data Management: Definitions and Standards for Expedited Reporting, ICH-E2A March 1995, as implemented by the U.S. Food and Drug Administration defines serious adverse event (SAE) or reaction as any untoward medical occurrence that at any dose:

- results in death;
- is life-threatening; (NOTE: The term "life-threatening" in the definition of "serious" refers to an event in which the patient was at risk of death at the time of the event; it does not refer to an event which hypothetically might have caused death if it were more severe.)
- requires inpatient hospitalization or prolongation of existing hospitalization;
- results in persistent or significant disability/incapacity; or
- is a congenital anomaly/birth defect.

An unexpected event is one that is not described with respect to nature, severity, or frequency in the current Investigator's Brochure or product package insert.

Any SAEs due to any cause, that occur during the course of this investigation, whether or not related to the investigational agent, must be reported within 24-hours by telephone to: the Study Medical Monitor, the NIDA Project Officer/Project Manager, the UCLA Coordinating Center, and the investigator-sponsor as follows:

NIDA Medical Monitor: [name]. [name]

NIDA Project Officer: [name], M.S., [name]

NIDA Project Manager: [name], RN, BC, M.S. [name]

Coordinating Center Principal Investigator: [name]., [name]

The telephone report is to be followed by submission of a completed SAE Form with demographic information and a narrative explanation of the event. Attached to the SAE Form should be photocopies of the AE Form, the Concomitant Medication Form, and the Medical History Form from the subject's CRFs. All serious medical events are also to be reported to the responsible IRB according to local regulatory requirements. All participating investigators will be notified of any serious and unexpected AE requiring submission to the FDA in an IND safety report from the investigator-sponsor.

Any fatal or life-threatening SAE that is investigational agent related and unexpected must be reported initially to the FDA within 7 calendar days via telephone, facsimile or e-mail with a written follow-up within an additional 8 calendar days. Any additional clinical information that is obtained must be reported, as it becomes available to the FDA.

The investigator-sponsor will inform NIDA of all SAEs that occur during the study. The investigator-sponsor is required by FDA regulations to report these to the FDA in a timely fashion. All AEs that are both serious and unexpected must be reported to the FDA, in writing, within 15 calendar days of notification of NIDA of the SAE.

There can be serious consequences including ultimately, criminal and/or civil penalties for sponsors who fail to comply with FDA regulations governing the reporting of SAEs to FDA. The study investigators in this study have the responsibility of promptly reporting all SAEs to NIDA and the investigator-sponsor in order that the investigator-sponsor can comply with these regulations.

If a study subject withdraws from the study or if an investigator decides to discontinue the subject from the study because of a SAE, the subject must have appropriate follow-up medical monitoring. If the subject is hospitalized, medical monitoring will consist of not less than daily evaluation by physical examination, vital signs, laboratory evaluations, and if applicable, ECG monitoring for significant treatment-emergent abnormalities. Monitoring will continue until the problem prompting hospitalization has resolved or stabilized with no further change expected or is discovered to be clearly unrelated to of investigational agents or progresses to death.

15 ANALYTICAL PLAN

15.1 PRIMARY OBJECTIVE

The primary objective of this study is to assess the efficacy of bupropion in reducing methamphetamine use in subjects with methamphetamine dependence (DSM-IV criteria).

15.2 SECONDARY OBJECTIVES

Secondary objectives include:

- 1. Determining the safety of bupropion in the study population.
- 2. Assessing the efficacy of bupropion in other measures of success in the reduction of methamphetamine use including the proportion of successful subjects with 3 consecutive weeks of negative urine samples as measured by 9 consecutive negative urine samples for methamphetamine, the weekly mean proportion of non-use days assessed by self report of use, the largest number of consecutive methamphetamine non-use days, and reductions in use as compared to baseline.
- 3. Assessing the efficacy of bupropion in the reduction in the severity of methamphetamine dependence (assessed by ASI-Lite and self and observer scored CGI), craving (assessed by BSCS), severity of withdrawal symptoms (assessed by MAWQ), and severity of depression (assessed by HAM-D) as compared to placebo control.
- 4. Assessing the efficacy of the bupropion in reducing the proportion of use-days of other substances of abuse (opiates, marijuana, cigarette smoking, alcohol, and cocaine) as determined by SUR and the number of negative urines for other substances of abuse (amphetamines, cocaine, opiates, tetrahydocannabinol, benzodiazepines, and barbiturates) by urine drug screen or negative alcohol breathalyzer tests.
- 5. Assessing the effects on HIV risk taking behaviors.
- 6. Assessing the effects of bupropion on neurocognitive functions.
- 7. Assessing the reduction in methamphetamine use as a function of the resolution of depression in bupropion versus placebo groups.

15.3 STATISTICAL HYPOTHESES

The null hypothesis is that bupropion treatment, compared to placebo, will result in a statistically significant difference (two-sided p < 0.05) in the weekly proportion of methamphetamine-free urines. Hypotheses for the secondary outcome measures include that bupropion treatment, compared to placebo, will reduce the pattern and quantity of methamphetamine use by various measures of success, reduce the severity of methamphetamine dependence (assessed by ASI-Lite and self and observer scored CGI), methamphetamine craving (assessed by BSCS), severity of

withdrawal symptoms (assessed by MAWQ), and depression (assessed by HAM-D), and decrease the amount of use-days of other substances of abuse (opiates, marijuana, nicotine, alcohol, and cocaine) as determined by self report of use or urine drug determination (amphetamines, cocaine, opiates, tetrahydrocannabinol, benzodiazepines, and barbiturates).

There is no generally accepted definition of clinically significant improvement in the treatment of methamphetamine dependency. The primary and secondary objectives are intended to explore various aspects of response to therapy and to help define a clinically meaningful response. The secondary objectives also add a measure of clinical relevance to the reduction of use by exploring the effect of therapy on psychosocial aspects of methamphetamine dependency.

15.4 OUTCOME MEASURES

15.4.1 Primary Outcome Measure

The primary outcome variable for each subject is the weekly proportion of methamphetamine– free urine samples. Three urine collection days are scheduled per calendar week. The weekly methamphetamine-free sample is recorded as "0" if all three urine samples in the week were less than 300 ng/ml. The weekly methamphetamine-free sample is recorded as "1" if the proportion of weekly methamphetamine-free samples is between 0.67 and 0.75, inclusive. The weekly methamphetamine-free sample is recorded as '2' if the proportion of weekly methamphetaminefree samples is between 0.33 and 0.5, inclusive. The weekly methamphetaminefree samples is between 0.33 and 0.5, inclusive. The weekly methamphetamine-free sample is recorded as "3" if the proportion of weekly methamphetamine-free samples is 0.

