SAFETY ASSESSMENTS: All candidates for study enrollment will have a physical examination, a 12-lead electrocardiogram (ECG), and clinical laboratory studies (blood chemistry, hematology, and urinalysis performed during screening. If the potential participant is female, a pregnancy test will also be performed during screening, at study weeks 4 and 8, and at study termination. Vital signs, concomitant medication use, and a urine screen for other substances of abuse will be assessed weekly during treatment. AEs will be assessed at each visit. At study termination (the last assessment visit after treatment completion or if the subject terminates prematurely), subjects will be evaluated for AEs, vital signs, physical examination, clinical laboratory studies, and ECG.

EFFICACY ASSESSMENTS: The primary outcome response measures will be the weekly proportion of methamphetamine-free urines during the 12 weeks of treatment. Secondary assessments include analyses of other measures of success in the reduction of methamphetamine use including the proportion of successful subjects with 3 consecutive weeks of negative urine samples as measured by 9 consecutive negative urine samples for methamphetamine, proportion of methamphetamine non-use days by self report, the largest number of consecutive methamphetamine non-use days, and reductions in use as compared to baseline. Additional

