was well tolerated and reduced self-reported craving for cocaine. A multicenter placebocontrolled double-blind clinical trial of bupropion for cocaine dependence in methadonemaintenance patients indicates efficacy of bupropion for the subgroup of patients with depression at study entry (Margolin *et al.*, 1995).

The results of animal studies designed to test the ability of bupropion to block effects of methamphetamine support clinical use for the treatment of methamphetamine dependence (Kim *et al.*, 2000). Thus, bupropion provides complete protection against methamphetamine-induced decrease in dopamine uptake in striatum in *in vitro* model of methamphetamine-induced dopamine nerve terminal toxicity. It is logical to postulate that combination of bupropion's dopaminergic activity and antidepressant properties may guarantee its efficacy in clinical trials for treatment and relief of the signs and symptoms of methamphetamine withdrawal and for prevention of the relapse.

Bupropion Pharmacokinetics. Tablets of bupropion hydrochloride come in immediate- and sustained-release (SR) formulations. The bupropion SR, 150 mg, twice daily formulation will be used for this study. Bupropion SR has been shown to be bioequivalent to 100 mg three times daily of the immediate release formulation with regards to rate and extent of absorption and parent drug and metabolites in clinical trials for depression. Better compliance is expected with twice daily dosing as opposed to thrice daily dosing making bupropion SR an obvious choice for study.

The half-life of bupropion is approximately 21 hours after chronic dosing. Peak plasma concentrations of bupropion are achieved within 3 hours following oral administration. It appears there is no clinically significant delay in absorption due to food. Steady state plasma concentrations of bupropion are reached within 8 days. Four basic metabolites have been identified. These metabolites are pharmacologically active, but their potency and toxicity relative to bupropion have not been totally characterized. They may be of clinical importance because the plasma concentration of metabolites is higher than those of bupropion.

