8.2 OUTCOME/RESPONSE MEASURES

The principal outcome measure is urine methamphetamine analysis. This outcome measure was selected as the primary study endpoint to examine the effect of treatment on an objective measure of reduction in methamphetamine use. However, as methamphetamine has an excretion half-life of 12 to 14 hours, carryover could result in a positive urine specimen even when the subject has not used. Therefore, this is potentially a conservative outcome measure of treatment effect.

Data from previous methamphetamine pharmacokinetic studies, as well as other outpatient studies, will be used to develop rules/algorithm for determining new versus old (carryover) use utilizing urine methamphetamine levels. As the urine samples in this study are being analyzed quantitatively for methamphetamine, if an algorithm is developed to determine new use versus carryover, this algorithm will be used for additional analyses.

Secondary outcome measures include:

- 1. Measuring reductions in drug use assessed by self-report of use;
- 2. Assessing the severity of methamphetamine dependence using the ASI-Lite and self and observer scored CGI;
- 3. Assessing changes in craving (determined BSCS);
- 4. Assessing the severity of withdrawal symptoms (determined by MAWQ),
- 5. Assessing changes in depression (determined by HAM-D score) and the association of these changes with reductions methamphetamine use;
- 6. Assessing the effect on the use days of other substances of abuse (opiates, marijuana, cigarette smoking, cocaine, and alcohol) as determined by self-report and negative urine (opiates, tetrahydrocannabinol, amphetamines, cocaine, benzodiazepines, or barbiturates) or alcohol breathalyzer results;
- 7. Assessing the effect on HIV risk taking behaviors;
- 8. Assessing the effect on cognitive functions; and
- 9. Safety of bupropion in the study population.

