12.4 TREATMENT PHASE

At the first clinic visit, subjects will be given instructions on how to administer the investigative agent, Bupropion or placebo, and will be given a one-week supply. This is a double-blind study in which neither the subject nor the site staff will know if the subject is receiving the investigational drug or the placebo. The subject will be given the first dose of the investigational agent in the clinic regardless of the time and will be observed for one hour to monitor for immediate adverse symptoms.

Subjects will be scheduled for treatment and assessment visits three times per week usually on a Monday, Wednesday, and Friday for 12 weeks. Two consecutive days may be scheduled around

holidays or other schedule conflicts. All subjects will be offered an opportunity for HIV testing and counseling and HIV/AIDS education (Appendix II). All subjects will be provided with CBT three times per week during the 12 weeks of treatment. Clinical evaluations are described in detail in section 12.

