13.3 ASSESSMENTS DURING TREATMENT

Over the 12-week period of treatment, subjects will return to the clinic three times per week (ideally on Monday, Wednesday, and Friday). Assessments will be performed as follows:

At each visit:

- 1. SUR
- 2. Urine methamphetamine and creatinine
- 3. Alcohol breathalyzer
- 4. AEs
- 5. MAWQ (the first two weeks only)

- 6. Concomitant medications
- 7. Treatment compliance (study agents and CBT)

Once per week preferably at the first visit of each week:

- 1. Urine toxicology screen using an onsite testing device
- 2. Urine toxicology screen (urine specimen sent to NWT for analysis)
- 3. BSCS
- 4. CGI-S
- 5. CGI-O
- 6. MAWQ (starting at week 3 for the first two weeks it is collected 3 times per week)
- 7. Vital signs

At weeks 4 and 8, preferably at the first visit of the week:

1. Pregnancy test

At week 2, 4, 6, 8, 10 and 12, preferably at the first visit of the week:

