13.6.23 Substance Use Report (SUR)

The SUR includes the subject's report of use of methamphetamine, marijuana, nicotine, alcohol, opiates, and cocaine use for each day of the week. The subject is asked to report any use during days since the last clinic visit. The day that the subject is reporting use is not scored until the subsequent visit as use may occur later in the day.

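### The primary weekly score counts the first-dose-visit urine, which can show only untreated use, among the week-1 samples; the dilution is small, but the scored weeks should be anchored to dosing

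*Protocol*

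**What the plan says.** The synopsis (section 3) gives the primary outcome as the "weekly proportion of methamphetamine-free urines during the 12 weeks of treatment". Section 15.4.1 states that "Three urine collection days are scheduled per calendar week" and codes each week. Code 0 applies if all three samples are below 300 ng/mL, code 1 if the methamphetamine-free proportion is 0.67 to 0.75, code 2 if it is 0.33 to 0.5, and code 3 if it is 0.

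Section 12.4 sets the schedule: "Subjects will be scheduled for treatment and assessment visits three times per week usually on a Monday, Wednesday, and Friday for 12 weeks". On the first of these visits, "The subject will be given the first dose of the investigational agent in the clinic regardless of the time". Section 13.3 lists "Urine methamphetamine and creatinine" under the assessments made at each visit and makes no exception for the first-dose visit. No section moves that urine to baseline or leaves it out of week 1.

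Sections 12.5 and 13.4 call for one more methamphetamine urine at termination, after the last dose in week 12. Neither these sections nor 15.4.1 says whether it enters the primary score.

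**The concern.** A urine looks backward. A sample taken at the visit where dosing starts shows use before treatment, or at most within the first hours after one dose, so randomised treatment cannot have influenced it. If it is scored in week 1, a third of that week's information carries no treatment contrast, and the best code is closed to anyone who arrives positive.

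The term calendar week adds a second looseness. Dosing and drug labelling run on study days and study weeks, while scoring is tied to the calendar. Nothing requires a Monday start, and for other starting days the codes do not fit the number of samples in the first and last calendar weeks.

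At stake are a small loss of sensitivity in the primary comparison and an endpoint window that two analysts could build differently.

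**Working it through.** **Number of treatment urines.** The Protocol prints no total, but the payment cap in section 12.10 fixes it. Payment is $10 per urine visit in screening and treatment, plus $25 each (as I read it) for termination and week 16.
- With 4 screening weeks: (4 × 3 + 12 × 3) × $10 + 2 × $25 = 48 × $10 + $50 = $530, the stated maximum.
- With 35 or 37 treatment urines the total would be $520 or $540.
- So there are 36 treatment-visit urines, and termination is paid separately.

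**Where they fall.** Treatment days 1 to 84, visits on Monday, Wednesday and Friday:

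| Start | Study days of the urines | Urines per calendar week |
|---|---|---|
| Monday | 1, 3, 5, 8 … 78, 80, 82 | 3 in each of 12 weeks |
| Wednesday | 1, 3, 6, 8 … 78, 80, 83 | 2 in the first, 3 in the next 11, 1 in a 13th |
| Friday | 1, 4, 6, 8 … 78, 81, 83 | 1 in the first, 3 in the next 11, 2 in a 13th |

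The day-1 urine is 1 of 36 overall (2.8%) and 1 of 3 in week 1 for a Monday start.

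**Effect on the code.** In a three-sample week the code equals 3 minus the number of negative samples. A subject positive on day 1 can have at most 2 negatives, a proportion of 0.67, so the best available code is 1.

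**Weeks without three samples.** Applying 15.4.1 literally:
- Two samples, both negative: no code, because code 0 requires all three.
- Four samples: 3/4 = 0.75 gives code 1 and 2/4 = 0.50 gives code 2; 1/4 = 0.25 and 4/4 have no code.

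**Dilution.** Section 15.7 gives no effect size or variance, so the following rests on assumptions: complete collection, no effect at the day-1 urine, a full and constant effect at the other 35, and a normal approximation to the ordinal GEE.
- Attenuation of the mean effect: 35/36 = 0.972.
- Equivalent sample size factor: (36/35)² = 1.058, about 6%.
- A design with 80% power (two-sided 5%): 2.802 × 35/36 − 1.960 = 0.764, giving 77.8%.
- A design with 90% power: 3.242 × 35/36 − 1.960 = 1.192, giving 88.3%.
- At 75 per arm with assumed standardised effects: 0.30 gives 45.1% falling to 43.1%; 0.50 gives 86.5% falling to 84.5%.

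**Dropout.** Section 15.7 reports 46%-50% dropout among the first fifty subjects, so early urines weigh more in the observed data. If, for illustration, half of the subjects left after week 6, the mean would be (36 + 18)/2 = 27 urines, and the day-1 share 1/27 = 3.7%. That is larger, but still small.

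**The case against.** The best case against is that this is minor and usually settled in a statistical analysis plan, which is not shown. Dilution acts equally in both arms, two of the three week-1 samples are post-dose, and the ordinal score still separates subjects at 2/3, 1/3 and 0. All of that stands, and it limits the weight of the point. The deferral argument is weaker here, because section 16.3 says the analysis will follow the analytical plan section of the Protocol, so 15.4.1 is the governing rule.

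Several stronger readings are tempting but not supported:
- *The termination urine is left unscored.* A reader might infer this because termination is listed and paid separately. No section says so. Its timing in week 12, and the bands that reach 0.75 and 0.5, suggest that a four-sample week was foreseen. The text is silent.
- *Calendar week 1 absorbs baseline urines after a midweek start.* The synopsis confines the outcome to the 12 treatment weeks. The first calendar week is then short, not contaminated.
- *The Protocol already makes this correction for self-report.* Section 13.6.23 says "The day that the subject is reporting use is not scored until the subsequent visit as use may occur later in the day". That postpones an incomplete day; it does not separate baseline from treatment.
- *The gain is much larger.* Omitting week 1 altogether would give an efficiency ratio of 1.08 to 1.18, if week 1 carried half to none of the later effect (assuming exchangeable correlation 0.5 and complete data). That is a different comparison from moving one urine.
- *Carry-over makes the second sample uninformative too.* Section 8.2 concedes that "as methamphetamine has an excretion half-life of 12 to 14 hours, carryover could result in a positive urine specimen" and calls the measure conservative. How often this matters depends on day-1 concentrations, which the Protocol does not give, and shifting by one visit would not cure it.

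**Conclusion.** The point holds as a small improvement. Followed literally, the Protocol scores the first-dose-visit urine in week 1 although it can reflect only untreated use, and it ties scored weeks to the calendar instead of to dosing. The cost is attenuation towards no difference: 2.8% of urines with complete collection, about 6% in efficiency, about 2 power points. It favours neither arm and does not inflate type I error. The size rests on the assumption of a full, constant effect elsewhere and on equal weight per urine; dropout raises it somewhat. The status of the termination urine is an ambiguity to resolve, not a demonstrated exclusion. The visit pattern was read from sections 12.4 and 13.3, because the treatment columns of Table 1 were not legible in the copy reviewed.

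**What to change.** In section 15.4.1:
- Replace calendar weeks by study weeks counted from the first dose.
- Treat the urine from the first-dose visit as a baseline sample, and form week 1 from the scheduled samples after it (days 3, 5 and 8 if weeks are to keep three samples).
- State whether the termination urine counts in week 12.
- Extend the codes so that weeks with two or four samples always receive one, including all-negative weeks and a proportion of 0.25.
- Add a supportive analysis of weeks 2-12, which fits the statement in section 4 that "Steady state plasma concentrations of bupropion are reached within 8 days".

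This changes definitions only. The samples are already scheduled, and it can be done before unblinding. The price is a choice: if the termination urine is not used, one week has only two samples; if it closes week 12, that sample depends on attendance at the termination visit, which may be informative with 46%-50% dropout. What it would add is use in about 2 to 3 of the 84 treatment days, so either choice is defensible if fixed in advance.

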15.6 ANALYSIS PLAN

15.6.1 Efficacy Assessments

Each of the primary and secondary efficacy outcome measures will be analyzed for the intent-totreat and for the evaluable population. Major differences in the results, if any, will be further explored. While there is every intent to be complete in describing the analyses to be performed, it is not possible to anticipate every contingency and some adjustments may be required to meet constraints posed by the structure of the data.

Statistical tests will be two-sided at a 5% Type I error rate. Confidence intervals will be two-sided with a 95% confidence coefficient.

Primary Efficacy Outcomes

The weekly mean proportion of methamphetamine-free urines on study will be compared between treatment groups using Generalized Estimating Equations (GEE) for ordinal categorical response (Lipsitz *et al.*, 1994). GEE provide a model-based regression method applicable for the analysis of the correlated data that will result from this repeated measures longitudinal study. The GEE procedure was first proposed by Liang and Zeger (1986) and Zeger and Liang (1986) and models the population average. GEE has several useful features:

- 1. It can be used to analyze different types of outcomes such as continuous, binary, or count.
- 2. It can be used to analyze an unbalanced design caused by either differing numbers of observations per person or by observations taken at different times.
- 3. The parameter estimates are consistent even if assumptions about the variance structure are not completely accurate.

As a secondary analysis, the individual effects, if any, of age, race, site, and usual route of methamphetamine use (oral/nasal inhalation versus intravenous/smoked) on the primary treatment effects will be determined where numbers permit. The first order interactions of these variables with gender, historical self-report of methamphetamine use (prior use in the last 30 days ≤ 18 versus > 18), and severity of depression (HAM-D score ≤ 12 versus >12) will also be included in the model. Presentation will include the full model with all terms and a reduced model containing only significant terms.

Secondary Efficacy Outcomes

Unless the primary response analysis implies the need for a more elaborate model, between group comparisons of the secondary outcomes will be performed as follows:

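### Protocol 15.4.1 gives no code to a clean week of one or two urine samples but codes an all-positive one as 3; this overstates use in each arm and biases the arm comparison if missed visits differ by arm

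*Protocol*

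**What the plan says.** Protocol 15.4.1 makes the primary outcome a weekly score from 0 to 3. "Three urine collection days are scheduled per calendar week". The rules are:

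- Code 0: "if all three urine samples in the week were less than 300 ng/ml".
- Code 1: "if the proportion of weekly methamphetamine-free samples is between 0.67 and 0.75, inclusive".
- Code 2: the proportion of methamphetamine-free "samples is between 0.33 and 0.5, inclusive".
- Code 3: "if the proportion of weekly methamphetamine-free samples is 0".

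Code 0 is a count of three. The other codes are proportions. Limits of 0.5 and 0.75 can arise only from weeks with two or four samples, so weeks without exactly three samples were foreseen.

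Section 15.6.1 analyses the score "using Generalized Estimating Equations (GEE) for ordinal categorical response" and says of the method: "It can be used to analyze an unbalanced design caused by either differing numbers of observations per person". Section 15.6.2 compares the number of missing observations between arms descriptively. Section 16.3 sends the analysis to the protocol's analytical plan section, which contains 15.4.1.

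**The concern.** Whether a short week can be scored depends on its own result. A subject who gives two samples and is positive on both scores 3. A subject who gives two samples and is clean on both gets no score.

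Short weeks should be expected. Section 12.6 attaches no penalty to missed sessions and treats a subject as a drop-out only after six consecutive misses. Someone who attends one visit every week stays in the trial and, even if always clean, can never score 0. Section 15.7 reports pooled, blinded dropout of 46%–50% in the first fifty randomized. That is dropout rather than scattered misses, but it does not suggest near-complete attendance.

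GEE accepts unequal numbers of observations. It does not restore weeks that were left unscored because they were clean. At stake are the level of the primary outcome in each arm and, if attendance differs by arm, the treatment comparison.

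**Working it through.** **Step 1. Apply the rules to every possible week.** Proportions are rounded to two decimals, so 2/3 falls in code 1 as intended. Entries are clean/provided.

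| Samples provided | Codes under 15.4.1 |
|---|---|
| 1 | 0/1 → 3; 1/1 → none |
| 2 | 0/2 → 3; 1/2 → 2; 2/2 → none |
| 3 | 0/3 → 3; 1/3 → 2; 2/3 → 1; 3/3 → 0 |
| 4 | 0/4 → 3; 1/4 → none; 2/4 → 2; 3/4 → 1; 4/4 → none |

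Full weeks code correctly. Among weeks of one to three samples, the only gaps are clean weeks. Four-sample weeks should be rare, because three are scheduled.

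**Step 2. How often weeks are short.** The protocol gives no missed-visit rate, so assume each of three visits is missed independently with probability m. Then P(1 or 2 samples | at least 1) = [1 − (1−m)³ − m³] / (1 − m³).

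- m = 10%: 0.270/0.999 = 27%
- m = 20%: 0.480/0.992 = 48%
- m = 30%: 0.630/0.973 = 65%

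**Step 3. Effect within one arm.** Assume 40% of subjects give clean samples 95% of the time and 60% give them 10% of the time. With m = 20%, the probabilities of 3, 2 and 1 samples are 0.512, 0.384 and 0.096.

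- Clean but uncoded weeks: 0.384 × (0.4×0.95² + 0.6×0.10²) + 0.096 × (0.4×0.95 + 0.6×0.10) = 0.141 + 0.042 = 18.3% of all weeks.
- Clean and coded 0: 0.512 × (0.4×0.95³ + 0.6×0.10³) = 17.6% of all weeks.
- Share of clean weeks with no code: 18.3/(18.3 + 17.6) = 51%.

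Among coded weeks, use itself being unchanged:

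| Attendance | Code 0 | Code 3 | Mean code |
|---|---|---|---|
| 100% | 34.4% | 43.7% | 1.68 |
| 80% | 21.7% | 57.5% | 2.10 |
| 70% | 16.2% | 64.7% | 2.29 |

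**Step 4. Effect between arms, same use mix in both.** Cumulative odds ratios at the three cut-points, favouring the better-attending arm:

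| Attendance | 15.4.1 as written | Every clean week coded 0 |
|---|---|---|
| 80% v 80% | 1.00 / 1.00 / 1.00 | 1.00 / 1.00 / 1.00 |
| 90% v 80% | 1.39 / 1.43 / 1.33 | 0.96 / 1.02 / 1.07 |
| 90% v 70% | 2.00 / 2.09 / 1.80 | 0.91 / 1.02 / 1.13 |

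With a true effect (50% v 40% of subjects mostly clean), full attendance gives 1.44 / 1.48 / 1.36 and 70% attendance in both arms gives 1.45 / 1.45 / 1.29. With 70% attendance in the better arm and 90% in the other, the direction reverses: 0.72 / 0.70 / 0.72.

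**Step 5. Type I error.** Assumptions: 75 per arm, 12 weeks, no difference in use, missed visits of 10% v 20%, mean clean about 50%, subject SD 1 to 4 and week SD 0.5 or 1 on the logit scale. Two tests stood in for the ordinal GEE.

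- Week-level cluster-robust test of the mean score: 24%–57%.
- t-test on subject mean scores: 7%–44%. The two-class mix of Step 3 gave 6%.
- Every clean week coded 0: about 5–6% (one run gave 6–7%).
- Missed visits of 15% v 20%: 9%–19% and 5%–15% for the two tests.
- Equal rates of 20% v 20%: about 5% under either rule.

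The two tests differ because the loss falls on the number of scored weeks that mostly abstinent subjects contribute. A test that weights weeks equally feels this more than one that weights subjects equally.

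**The case against.** The strongest reply is that discarding clean short weeks is the harshest reading. Section 15.4.1 opens by defining the outcome as a weekly proportion and says three collections are scheduled. The count in code 0 may simply describe a full week at proportion 1. On that reading every clean week scores 0 and the one-sided loss disappears. An analysis plan that is not shown may say so. This stands as a view of intent. It does not stand as a defence of the text, which states a count for code 0 where the neighbouring codes state proportions.

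A reader might infer that missed visits by themselves bias the treatment comparison. The documents do not support that. With equal random attendance the odds ratio is 1.00 at every cut-point, the test keeps its level, and a true effect is little changed. A reader might also take one simulated error rate as the expected size. That is not supported either: the attendance gap is assumed, the result moves widely with the assumed variance and the test, and neither test is the planned GEE.

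Sections 15.3 and 15.7 also describe partly exploratory aims and a sample size not based on power. Secondary measure E, the overall proportion of negative urines, does not use the 0–3 code and could expose an artefact. Both points limit the damage, but neither corrects the primary score.

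**Conclusion.** The coding defect is certain and follows from the text alone: 1/1 and 2/2 clean have no code while 0/1 and 0/2 score 3, and 4/4 and 1/4 are also uncoded. Wherever visits are missed, the score overstates use within each arm. Under the use mix assumed above, 80% attendance moves the mean code from 1.68 to 2.10.

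Bias between arms is conditional. It needs missed visits that differ by arm, or that relate to use differently by arm. The protocol gives no attendance by arm, so neither size nor direction can be stated. At an assumed 10% v 20%, type I error ran from about 7% to 57%, against about 5–6% after the fix.

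This should be corrected before analysis because it is a stated rule on the primary endpoint. The inverted null in sections 5.1 and 15.3 ("The null hypothesis is that bupropion treatment, compared to placebo, will result in a statistically significant difference") is a genuine drafting error, but it is separate and adds no weight here: 15.6.1 states the two-sided 5% test clearly.

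**What to change.** In 15.4.1, before unblinding, define p = clean samples / samples provided in the week, and score:

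- 0 if p = 1
- 1 if 0.5 < p < 1
- 2 if 0 < p ≤ 0.5
- 3 if p = 0
- no score if no sample was provided

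This keeps the present codes for 3/3, 2/3, 1/3 and 0/3 and assigns 1/1, 2/2, 4/4 and 1/4. It removes the one-sided loss but does not make the score wholly independent of the number of samples, because short weeks fall more often in the extreme codes. At 90% v 70% attendance the remaining odds ratios were 0.91 / 1.02 / 1.13 under the two-class mix. They were 0.51 / 1.17 / 1.56 if every sample were independently clean with probability 40%. Samples per week should therefore be reported by arm beside the primary result.

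As a separate one-line correction, restate the null in 5.1 and 15.3 as no difference between arms in this score.

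The cost is a few lines of text and no new data.
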